1.6 Product Development Background

1.6.1 Clinical Summary

1.6.1.1 Summary of Nivolumab Clinical Pharmacokinetics

The pharmacokinetics (PK) of nivolumab were studied in subjects over a dose range of 0.1 to 10 mg/kg administered as a single dose or as multiple doses of nivolumab every 2 or 3 weeks. The geometric mean (% CV%) clearance (CL) was 9.5 mL/h (49.7%), geometric mean volume of distribution at steady state (Vss) was 8.0 L (30.4%), and geometric mean elimination half-life (t_{1/2}) was 26.7 days (101%). Steady-state concentrations of nivolumab were reached by 12 weeks when administered at 3 mg/kg Q2W, and systemic accumulation was approximately 3-fold. The exposure to nivolumab increased dose proportionally over the dose range of 0.1 to 10 mg/kg administered every 2 weeks. The clearance of nivolumab increased with increasing body weight. The PPK analysis suggested that the following factors had no clinically important effect on the CL of nivolumab: age (29 to 87 years), gender, race, baseline LDH, PD-L1. A PPK analysis suggested no difference in CL of nivolumab based on age, gender, race, tumor type, baseline tumor size, and hepatic impairment.

Although ECOG status, baseline glomerular filtration rate (GFR), albumin and body weight had an effect on nivolumab CL, the effect was not clinically meaningful. Additionally, PPK and exposure response analyses have been performed to support use of 240 mg Q2W dosing in addition to the 3 mg/kg Q2W regimen. Using the PPK model, exposure of nivolumab at 240 mg flat dose was identical to a dose of 3 mg/kg for subjects weighing 80 kg, which was the approximate median body weight in nivolumab clinical trials (see [Section 1.3.1.1](#)).

Full details on the clinical pharmacology aspects of nivolumab can be found in the Investigator Brochure.

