It is possible that unforeseen or unanticipated adverse events may occur. In order to minimize the overall risks to participating subjects, the protocol has inclusion-exclusion criteria appropriate to the population, and specific follow-up safety assessments. Adverse events and serious adverse events will be reviewed on an ongoing basis by the Medical Monitor and the Sponsor's pharmacovigilance group to look for trends and safety concerns. Additionally, to ensure subjects' safety, an independent Data Monitoring Committee (DMC) will also be established to monitor the

safety of subjects treated with the combination regimens regularly and identify any early safety signal.

Recent safety concerns of increased risk of mortality and severe adverse events have been reported from two studies with pembrolizumab, an anti-PD-1 monoclonal antibody not approved for treatment of multiple myeloma, in combination with IMiD (lenalidomide and pomalidomide) and dexamethasone (<https://www.fda.gov/Drugs/DrugSafety/ucm574305.htm>). In light of these safety concerns, on 1 September 2017 the FDA requested that CA209602 be placed on partial clinical hold. As a consequence, as of 1-September-2017, enrollment in this study was stopped, as well as the cross-over of subjects randomized to the Pd control arm into the exploratory NE-Pd arm. Subjects on treatment as of 1-September-2017 who were deriving clinical benefit can continue treatment and must be monitored as per protocol requirements. As of Revised Protocol 02, the exploratory NE-Pd arm is removed from the study design, and enrollment in the study is focused on the investigational (N-Pd) and control (Pd) arms.

At FDA request, an interim PFS futility analysis based on the 12- April- 2018 database lock was performed to compare PFS between NPd and Pd arms. Based on the results of this futility analysis, on 23-August-2018 Bristol-Myers Squibb (BMS) has decided to permanently discontinue enrollment into the study due to insufficient evidence. The number of deaths that have occurred in the Arm NEPd (50%) were higher compared to those in the Arm NPd (29%) and Arm Pd (23%).

Three additional subjects in Arm Pd who crossed over to Arm NE-Pd have died due to disease progression, resulting in a total of 19 (27%) deaths in Arm Pd.

Among all treated subjects, the rates of serious adverse events [SAE] were higher in patients in Arm N-Pd (58%) and Arm NE-Pd (63%) compared to patients in Arm Pd (50%).

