3 INVESTIGATIONAL PLAN

3.1 Study Design and Duration

This is a phase 3 multicenter, randomized, open label study designed to evaluate the clinical benefit and safety of the combination therapy of Nivolumab, pomalidomide, and dexamethasone (N-Pd the investigational arm A), when compared to pomalidomide and dexamethasone (Pd; the control arm B) in subjects with relapsed and/or refractory multiple myeloma (rrMM).

Up to Revised Protocol 01, the study design included an exploratory third arm evaluating the clinical benefit and the safety of the combination therapy of elotuzumab, nivolumab, pomalidomide and dexamethasone (NE-Pd, the exploratory arm-[arm C]) in the same patient population. Additionally, subjects randomized to the Pd arm were allowed to cross over to this exploratory NE-Pd arm at the time of progression. Cross over was stopped as of 1 September 2017.

Enrollment in the NE-Pd exploratory arm was stopped as of Revised Protocol 02. All subjects already randomized to the NE-Pd arm, or who crossed over from the Pd to the NE-Pd arm will continue on study as long as they have clinical benefit and do not meet the study discontinuation criteria.

[figure not shown]
Initially, the study was designed to enroll approximately 417 subjects for a total of 348 subjects to be randomized (assuming 20% screen failure rate) to N-Pd and Pd arms in a 1:1 ratio. Randomization was performed with the following stratification factors: a) number of lines of prior therapy (2 vs 3+); AND b) ISS stage (1-2 vs 3).

Subjects were to continue treatment as long as the subject has clinical benefit from the treatment and does not meet criteria for treatment discontinuation.

As of 23-August-2018, any additional enrollment of CA209602 study was permanently closed due to the insufficient benefit observed based on the interim futility analysis of PFS. A total of 170 subjects were randomized into the study: 75 to NPd, 71 to Pd and 24 to NE-Pd arms. Subjects randomized to the NPd or NEPd arms may continue treatment based on investigator's judgement of continued clinical benefit. Study will be closed after all subjects complete safety follow-up (i.e., 100 days after the last subject has discontinued study treatment).

The study design schematic is presented in Figure 3.1-1.

Figure 3.1-1: Study Design Schematic

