- g) Subject Re-enrollment: This study permits the re-enrollment of a subject that has discontinued the study as a pre-treatment failure (ie, subject has not been randomized / has not been treated). If re-enrolled, the subject must be re-consented

3. Age and Reproductive Status

- a) Males and Females at least 18 years or legal age of consent per local regulations

- b) Women of childbearing potential (WOCBP) must have two negative serum or urine pregnancy tests (minimum sensitivity 25 mIU/mL or equivalent units of HCG). One 10-14 days prior to start of the study drug and one within 24 hours prior to the start of study drug
 - i) WOCBP must agree to follow instructions for method(s) of contraception from the time of enrollment for the duration of treatment with study drug plus 5 half-lives of study drug plus 30 days (duration of ovulatory cycle) for a total of 23 weeks (except the Pd arm- where only 4 weeks is required) post treatment completion
 - ii) Men who are sexually active with WOCBP must agree to follow instructions for method(s) of contraception for the duration of treatment with study drug plus 5 half-lives of study drug plus 90 days (duration of sperm turnover) for a total of 31 weeks (except the Pd arm -where only 4 weeks is required) post-treatment completion
- c) Women must not be breastfeeding
- d) Male patients must not donate sperm, for up to 7 months (4 weeks only for Pd arm) post treatment completion
- e) Azoospermic males and WOCBP who are not heterosexually active are exempt from contraceptive requirements. However they must still undergo pregnancy testing as described in this section
- f) All subjects must not donate blood for 90 days post treatment completion
- g) All subjects must be willing and able to comply with Pomalyst® REMS program, where applicable
- h) All subjects must agree not to share study medication

Investigators shall counsel WOCBP and male subjects who are sexually active with WOCBP on the importance of pregnancy prevention and the implications of an unexpected pregnancy. Investigators shall advise WOCBP and male subjects who are sexually active with WOCBP on the use of highly effective methods of contraception. Highly effective methods of contraception have a failure rate of < 1% when used consistently and correctly.

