6.4 Pregnancy

If, following initiation of the study drug , it is subsequently discovered that a study subject is pregnant or may have been pregnant at the time of study exposure, including during at least time to washout plus one ovulatory cycle (30 days) for a total of 23 weeks, or plus one spermatogenesis cycle (90 days) for a total of 31 weeks after product administration (for patients in arms A and C; 4 week duration needed for arm B), the investigator must immediately notify the BMS Medical Monitor/designee of this event and complete and forward a Pregnancy Surveillance Form to BMS Designee within 24 hours of awareness of the event and in accordance with SAE reporting procedures described in [Section 6.1.1](#). Refer to pomalidomide pregnancy risk prevention plan for additional information ([Appendix 6](#)).

In most cases, the study drug will be permanently discontinued in an appropriate manner (eg, dose tapering if necessary for subject safety). Please call the BMS Medical Monitor within 24 hours of awareness of the pregnancy.

The investigator must immediately notify the BMS (or designee) Medical Monitor of this event and complete and forward a Pregnancy Surveillance Form to BMS (or designee) within 24 hours of awareness of the event and in accordance with SAE reporting procedures described in [Section 6.1.1](#).

Follow-up information regarding the course of the pregnancy, including perinatal and neonatal outcome and, where applicable, offspring information must be reported on the Pregnancy Surveillance Form.

Any pregnancy that occurs in a female partner of a male study participant should be reported to BMS. Information on this pregnancy will be collected on the Pregnancy Surveillance Form.

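### The 23- and 31-week contraception windows are 2.5 and 6.5 days shorter than the protocol's own half-life formula gives, and no section says which window applies to Pd subjects who crossed over to nivolumab

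*Combined protocol and SAP*

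**What the plan says.** Section 3.3.1 builds the post-treatment contraception window from a formula. For women of childbearing potential, 3(b)(i) extends contraception beyond treatment by a period given as "plus 5 half-lives of study drug plus 30 days (duration of ovulatory cycle) for a total of 23 weeks". For men with partners of childbearing potential, 3(b)(ii) uses the same five half-lives, "plus 90 days (duration of sperm turnover) for a total of 31 weeks". Both items shorten the period to 4 weeks for the Pd arm, in 3(b)(i) with the words "for a total of 23 weeks (except the Pd arm- where only 4 weeks is required". Criterion 3(d) sets a separate rule on sperm donation: "Male patients must not donate sperm, for up to 7 months (4 weeks only for Pd arm) post treatment completion".

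Section 6.4 uses the same 23 and 31 weeks for pregnancy notification and assigns them by arm: "for patients in arms A and C; 4 week duration needed for arm B".

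The formula names neither a drug nor a half-life. Section 1.6.1.1 says that the geometric mean elimination half-life of nivolumab "was 26.7 days (101"; the figure in parentheses is the coefficient of variation in percent. The document gives no half-life for elotuzumab.

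On crossover, Section 3.1 let Pd subjects move at progression to NE-Pd, which contains nivolumab (Table 4.5.1.3-1), until 1 September 2017. It says that subjects randomised to NE-Pd "or who crossed over from the Pd to the NE-Pd arm will continue on study" while they benefit. Section 1.7 reports: "Three additional subjects in Arm Pd who crossed over to Arm NE-Pd have died due to disease progression". It adds those deaths to the Arm Pd total.

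**The concern.** A site will apply the number of weeks, not the formula behind it. If the totals do not follow from the formula and the half-life that the protocol reports, nobody can tell whether the period was computed from another half-life, rounded down, or mistyped. The sperm-donation limit adds a third figure for what looks like the same washout in men, and it is worded as a maximum.

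The crossover question is the larger one in days. The short window is tied to an arm label and not to the drugs received. A Pd subject who crossed over has had nivolumab, and the protocol uses the arm label for such subjects in two ways. These rules are still in force: enrolment is closed, but subjects in the nivolumab arms may stay on treatment and crossed-over subjects remain on study. At stake are the contraception and sperm-donation precautions and, for female subjects, the notification period of Section 6.4.

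**Working it through.** **Inputs.** Half-life 26.7 days (Section 1.6.1.1). Five half-lives and a further 30 or 90 days; totals of 23 and 31 weeks; 4 weeks for Pd; seven months for sperm donation (Section 3.3.1).

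**1. Formula against totals.** Days = 5 × half-life + 30 (women) or + 90 (men); 5 × 26.7 = 133.5.

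| | Formula | Weeks | Stated | Shortfall |
|---|---|---|---|---|
| Women | 133.5 + 30 = 163.5 days | 23.36 | 23 × 7 = 161 days | 2.5 days (1.6%) |
| Men | 133.5 + 90 = 223.5 days | 31.93 | 31 × 7 = 217 days | 6.5 days (3.0%) |

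**2. Can the stated totals be reproduced?** With 26.7 days:
- dropping the part-week gives 23 and 31, the stated pair;
- rounding to the nearest week gives 23 and 32;
- rounding up gives 24 and 32.

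So 26.7 days yields both totals only if the part-week is discarded, which leaves each one below the formula.

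**3. Which other half-lives fit?** Read as exact days, the totals imply (161 − 30)/5 = 26.2 days and (217 − 90)/5 = 25.4 days. Allowing for rounding:
- Rounding up, 23 weeks needs a half-life above 24.8 and up to 26.2 days, and 31 weeks one above 24.0 and up to 25.4. Both hold above 24.8 and up to 25.4. For example, 25 days gives 155 days (22.1 weeks) and 215 days (30.7 weeks).
- To the nearest week, the ranges are about 25.5 to 26.9 and 24.7 to 26.1 days, which overlap from about 25.5 to 26.1.

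Either explanation is possible. Neither half-life is stated.

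**4. Sperm donation.** 7 × 30.4 = about 213 days, and no run of seven calendar months exceeds 215. That is about 4 days below the 217 days of 3(b)(ii). Criterion 3(d) gives no formula, so the comparison that the text itself supports is seven months against 31 weeks.

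**5. Which window applies after crossover?**
- For Arm Pd: Section 1.7 adds the three crossover deaths to reach 19 (27%). 19/71 = 26.8%, so the denominator is the 71 subjects randomised to Pd. Sections 8.3.3 and 8.4.2.3 also treat crossed-over subjects separately from the NE-Pd arm.
- For Arm C: the Synopsis and Section 3.1 describe them as having crossed to the NE-Pd arm, and Section 4.5.1.3, headed as Arm C, is the only NE-Pd dosing text.

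Read as Arm C, they have 161 or 217 days. Read by randomised arm, they have 28 days, which is 161 − 28 = 133 or 217 − 28 = 189 days less, and about 28/26.7 = 1.05 nivolumab half-lives.

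**The case against.** On the half-life, the gaps are 1.6% and 3.0% of the stated windows, and the half-life is a geometric mean with a 101% coefficient of variation. The formula refers to study drug in general, so putting in 26.7 days is an inference, though nivolumab is the only drug on which the formula can be checked. Section 1.6.1.1 also gives clearance of 9.5 mL/h and a volume of 8.0 L. In a one-compartment approximation these imply ln 2 × 8.0/0.0095 = 584 hours, or 24.3 days, and windows of 151.6 and 211.6 days, both inside the stated totals. This stands as a reason to treat the shortfall as small. It does not settle it: the protocol reports 26.7 days, and 24.3 days rounded up gives 22 and 31 weeks, so it does not reproduce the pair either.

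On crossover, the natural reading may be that these subjects joined Arm C and took its rules. The rule is drug-based in its logic, the protocol elsewhere says randomised when it means randomised, and the Section 1.7 count is a death tally, not a contraception rule. Section 4.4.1 places crossover instructions in the IWRS manual, which is not among the documents. All of this stands. A reader might infer that the protocol tells sites to release nivolumab-exposed subjects at 4 weeks. It does not; it leaves the point open.

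A reader might also infer that any pregnancy in the gap would go unreported. The documents do not support that:
- Section 6.4 asks for pregnancies in partners of male subjects with no time limit.
- Its window for subjects is worded as a minimum.
- Tables 5.1-3 and 5.1-4 schedule pregnancy tests at 30 and 100 days after treatment with no exception by arm.
- Section 6.1 has pregnancy handled as an SAE, and Section 6.1.1 collects SAEs for 100 days after dosing stops.

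Any gap in the notification rule is therefore confined to female subjects.

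**Conclusion.** The concern holds as an inconsistency and an ambiguity. With the protocol's only nivolumab half-life, the stated windows are 2.5 days (women) and 6.5 days (men) below the formula. The men's total fails even nearest-week rounding, and the sperm-donation limit is about 4 days below the men's contraception window. These are small differences, and they rest on reading study drug as nivolumab at 26.7 days.

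The unanswered crossover question weighs more, because the two readings differ by 133 or 189 days. At least three subjects crossed over, but those three have died. The number who crossed over, and how many are still within any window, is not given, so the practical reach cannot be sized. It would also be going too far to conclude from this arithmetic that a particular window is clinically inadequate or correct; it shows only that the passages do not agree.

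**What to change.** The sponsor should reconcile Section 1.6.1.1, Section 3.3.1 items 3(b)(i), 3(b)(ii) and 3(d), and Section 6.4. The half-life used, the drug it belongs to, the rounding, the week totals and the sperm-donation period should then agree. The protocol should also state explicitly which window governs Pd subjects who crossed over to NE-Pd, and use the same statement in Sections 3.3.1 and 6.4. The IWRS manual and consent document should be checked against it. Which half-life, period or window is chosen is a clinical decision for the sponsor.

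The cost is wording in a few sections and a notice to sites. No analysis changes.

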At a minimum, subjects must agree to the use of two methods of contraception, with one method being highly effective and the other method being either highly effective or less effective as listed in the informed consent document.

3.3.2 *Exclusion Criteria*

1. Target Disease Exceptions

- a) Subjects with solitary bone or extramedullary plasmacytoma as the only evidence of plasma cell dyscrasia
- b) Subjects with monoclonal gammopathy of undetermined significance (MGUS), smoldering multiple myeloma (SMM), primary amyloidosis (without active multiple myeloma), Waldenstrom's macroglobulinemia, or POEMS syndrome (plasma cell dyscrasia with poly neuropathy, organomegaly, endocrinopathy, monoclonal protein, and skin changes)

- c) Subjects with active plasma cell leukemia (defined as either 20% of peripheral blood white blood cell count comprised of plasma/CD138+ cells or an absolute plasma cell count of $2 \times 10^9/L$)

2. Medical History and Concurrent Diseases

- a) Women who are of childbearing potential not complying to the above described contraceptive measures or are breastfeeding, and sexually active fertile men whose partners are WOCBP if they are not complying to the above described contraceptive measures
- b) Any uncontrolled or severe cardiovascular or pulmonary disease determined by the investigator, including:
 - i) NYHA functional classification III or IV, congestive heart failure, unstable or poorly controlled angina, uncontrolled hypertension, serious arrhythmia, or myocardial infarction in the past 12 months
 - ii) Subjects with interstitial lung disease that is symptomatic or may interfere with the detection or management of suspected drug-related pulmonary toxicity
- c) Active systemic infection
- d) Subjects with an active, known or suspected autoimmune disease. Subjects with type I diabetes mellitus, hypothyroidism only requiring hormone replacement, skin disorders (such as vitiligo, psoriasis, or alopecia) not requiring systemic treatment, or conditions not expected to recur in the absence of an external trigger are permitted to enroll
- e) Subjects with a condition requiring systemic treatment with either corticosteroids (> 10 mg daily prednisone equivalent) or other immunosuppressive medications within 14 days of initiation of study drug. Inhaled or topical steroids, and adrenal replacement steroid doses > 10 mg daily prednisone equivalent, are permitted in the absence of active autoimmune disease

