2.3 Contraception

2.3.1 Female Subjects of childbearing Potential

Females of childbearing potential enrolled in this protocol must agree to use two reliable forms of contraception simultaneously or to practice complete abstinence (True abstinence is acceptable when this is in line with the preferred and usual lifestyle of the subject. Periodic abstinence [eg calendar, ovulation, symptothermal or post-ovulation methods] and withdrawal are not acceptable methods of contraception.) from heterosexual contact during the following time periods related to this study: 1) for at least 28 days before starting pomalidomide; 2) while taking pomalidomide; 3) during dose interruptions; and 4) for at least 28 days after the last dose of pomalidomide.

The two methods of reliable contraception must include one highly effective method and one additional effective (barrier) method. If the below contraception methods are not appropriate for the FCBP, she must be referred to a qualified provider of contraception methods to determine the medically effective contraception method appropriate to the subject. The following are examples of highly effective and additional effective methods of contraception:

- Examples of highly effective methods:
 - Intrauterine device (IUD)
 - Hormonal (birth control pills, injections, implants, levonorgestrel-releasing intrauterine system [IUS], medroxyprogesterone acetate depot injections, ovulation inhibitory progesterone-only pills [e.g. desogestrel])
 - Tubal ligation
 - Partner's vasectomy
- Examples of additional effective methods:
 - Male condom
 - Diaphragm
 - Cervical Cap

Because of the increased risk of venous thromboembolism in subjects with multiple myeloma taking pomalidomide and dexamethasone, combined oral contraceptive pills are not recommended. If a subject is currently using combined oral contraception the subject should switch to another one of the effective methods listed above. The risk of venous thromboembolism continues for 4 to 6 weeks after discontinuing combined oral contraception. The efficacy of contraceptive steroids may be reduced during co-treatment with dexamethasone.

Implants and levonorgestrel-releasing intrauterine systems are associated with an increased risk of infection at the time of insertion and irregular vaginal bleeding. Prophylactic antibiotics should be considered particularly in subjects with neutropenia.

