2.3.2 Male Subjects

Male subjects must practice complete abstinence (True abstinence is acceptable when this is in line with the preferred and usual lifestyle of the subject. Periodic abstinence [eg calendar, ovulation, symptothermal or post-ovulation methods] and withdrawal are not acceptable methods of contraception.) or agree to use a condom during sexual contact with a pregnant female or a FCBP while taking pomalidomide, during dose interruptions and for at least 28 days after the last dose of pomalidomide, even if he has undergone a successful vasectomy.

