2.5.1.2 Male Subjects

Male subjects must agree to practice complete abstinence (True abstinence is acceptable when this is in line with the preferred and usual lifestyle of the subject. Periodic abstinence [eg calendar, ovulation, symptothermal or post-ovulation methods] and withdrawal are not acceptable methods of contraception.) or agree to use a condom during sexual contact with a pregnant female or a FCBP while taking pomalidomide, during dose interruptions and for at least 28 days after the last dose of pomalidomide, even if he has undergone a successful vasectomy.

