2.5.2 During and After Study Participation

2.5.2.1 Female Subjects:

- Females of childbearing potential with regular or no menstrual cycles must agree to have pregnancy tests weekly for the first 28 days of study participation and then every 28 days while taking pomalidomide, at study discontinuation, and at Day 28 following the last dose of pomalidomide.
- Females of childbearing potential with irregular menstrual cycles must agree to have pregnancy tests weekly for the first 28 days of study participation and then every

- 14 days while taking pomalidomide, at study discontinuation, and at Days 14 and 28 following the last dose of pomalidomide.
- At each visit, the Investigator must confirm with the FCBP that she is continuing to use two reliable methods of birth control if not committing to complete abstinence, or confirm commitment to complete abstinence.
- If a FCBP considers the need to change or to stop a method of contraception, the Investigator must be notified immediately.
- Counseling about pregnancy precautions and the potential risks of fetal exposure must be conducted at a minimum of every 28 days.
- If pregnancy or a positive pregnancy test does occur in a subject, pomalidomide must be immediately discontinued.
- Pregnancy testing and counseling must be performed if a subject misses her period or if her pregnancy test or her menstrual bleeding is abnormal. Pomalidomide must be discontinued during this evaluation.
- Females must agree to abstain from breastfeeding while taking pomalidomide and for at least 28 days after the last dose of pomalidomide.

2.5.2.2 *Male Subjects:*

- Must practice complete abstinence (True abstinence is acceptable when this is in line with the preferred and usual lifestyle of the subject. Periodic abstinence [eg calendar, ovulation, symptothermal or post-ovulation methods] and withdrawal are not acceptable methods of contraception.) or use a condom during sexual contact with a pregnant female or a FCBP while receiving pomalidomide, during dose interruptions and for at least 28 days after the last dose of pomalidomide, even if he has undergone a successful vasectomy.
- Must not donate semen or sperm while receiving pomalidomide, during dose interruptions or for at least 28 days after the last dose of pomalidomide.
- Counseling about pregnancy precautions and the potential risks of fetal exposure must be conducted at a minimum of every 28 days

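### Criterion 3(e) exempts azoospermic men from contraception without excepting pomalidomide, which contradicts the Appendix 6 condom-or-abstinence rule (minor, because the pregnancy programme in effect controls)

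*Combined protocol and SAP*

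**What the plan says.** Four parts of the main text bear on men and contraception.

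- Section 3.3.1, criterion 3(b)(ii): "Men who are sexually active with WOCBP must agree to follow instructions for method(s) of contraception". The period after treatment is 31 weeks, or 4 weeks in the Pd arm.
- Section 3.3.1, criterion 3(e): "Azoospermic males and WOCBP who are not heterosexually active are exempt from contraceptive requirements". Neither pomalidomide nor Appendix 6 is mentioned.
- Section 3.3.1, criterion 3(g): "All subjects must be willing and able to comply with Pomalyst® REMS program, where applicable".
- Section 3.3.2, exclusion 2(a), excludes "sexually active fertile men whose partners are WOCBP if they are not complying to the above described contraceptive measures".

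The Synopsis puts pomalidomide 4 mg on Days 1-21 in all three arms. Section 1.7 makes full participation in the pregnancy prevention programme a condition of being in the trial. Section 4.2.1 allows dispensing only to subjects who satisfy every condition of the local programme or of Appendix 6.

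Appendix 6, Section 2.3.2, tells male subjects to abstain or use a condom with a pregnant or potentially childbearing partner. The duty runs through treatment, through dose interruptions and "for at least 28 days after the last dose of pomalidomide, even if he has undergone a successful vasectomy". The introduction to the appendix limits it to certain countries or regions and requires everyone else to follow the local programme.

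**The concern.** A man with azoospermia who takes pomalidomide meets two instructions. The eligibility criteria tell him that he is outside the contraceptive requirements. Appendix 6, where it applies, tells him to abstain or use a condom, and it applies that rule even to men who have had a successful vasectomy, whose infertility does not release them. The condom rule also covers contact with a partner who is already pregnant, so it does more than prevent conception, and the reason for exempting infertile men does not carry over to it. Section 2.2.3 of the appendix says that the effect on sperm development and the risk to an unborn child through a male partner are unknown.

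At stake is the advice given on a suspected teratogen. A site that relies on 3(e) could tell such a man that he needs no precaution, and then have to sign a form with him that says the reverse. No endpoint, dataset or analysis is affected.

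**Working it through.** The plan states no figure on this point, so the check is a comparison of texts, followed by a crude ceiling on the number of subjects.

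**1. Does Appendix 6 exempt azoospermia anywhere?** It addresses men and condoms in five places.

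| Appendix 6 location | Placed under | Abstinence or condom rule | Interruptions and 28 days | Even after vasectomy | Azoospermia exempt |
|---|---|---|---|---|---|
| 2.2.3 | Counseling | Counselling item on condoms only | Not stated | Yes | No |
| 2.3.2 | Contraception | Yes | Yes | Yes | No |
| 2.5.1.2 | Pregnancy precautions | Yes | Yes | Yes | No |
| 2.5.2.2 | Pregnancy precautions | Yes | Yes | Yes | No |
| Section 3, male form | Counselling document | Yes | Yes | Yes | No |

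The full rule appears 4 times and the counselling item once. The vasectomy extension appears in 5 of 5, an azoospermia exemption in 0 of 5. The wording barely varies; Section 2.5.1.2, for example, has men "agree to use a condom during sexual contact with a pregnant female or a FCBP while taking pomalidomide, during dose interruptions".

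**2. Is the Appendix 6 rule something that 3(e) could be taken to waive?** Two features suggest so. Section 2.3.2 stands under "2.3 Contraception", although only one of the five places does. Also, 3(b)(ii) asks for 4 weeks after treatment in the Pd arm, and 4 x 7 = 28 days is the Appendix 6 period. Pd contains only pomalidomide and dexamethasone, so in that arm the requirement lifted by 3(e) appears to be the pomalidomide precaution itself. This is an inference from matching durations, not a statement in the plan.

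**3. Could the qualifier about heterosexual activity also apply to the azoospermic men?** If it did, the conflict would disappear, because a man without heterosexual contact has no contact that the condom rule covers. It is not the natural reading. Criterion 3(b)(ii) already binds only men who are sexually active with women of childbearing potential, so the male exemption would add nothing. Exclusion 2(a) also confines itself to fertile men, which fits an exemption based on infertility.

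**4. Which text controls?** Sections 1.7 and 4.2.1, criterion 3(g) and the Appendix 6 introduction make the programme compulsory. Appendix 6, Section 1, requires a signed counselling form before each supply, and the male form bars dispensing to a man who does not want to follow the precautions. None of these names 3(e), but a man who relies on 3(e) does not satisfy every programme condition. In effect the programme prevails.

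**5. Ceiling on numbers.** The Synopsis gives 75 N-Pd + 71 Pd + 24 NE-Pd = 170 randomized. Section 1.7 gives deaths of 29% in N-Pd, 50% in NE-Pd and 19 (27%) in Pd. Assuming that the percentages are of randomized subjects:

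- N-Pd: 0.29 x 75 = 21.75, so 22 deaths (22/75 = 29.3%); 75 - 22 = 53 remain.
- NE-Pd: 0.50 x 24 = 12 deaths; 24 - 12 = 12 remain.
- Pd: 19 deaths (19/71 = 26.8%); 71 - 19 = 52 remain.
- Total: 53 + 12 + 52 = 117, of whom 53 + 12 = 65 are in the two arms named as allowed to continue treatment.

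Without that assumption only the 19 Pd deaths are a firm count, and the limit is 170 - 19 = 151. All these figures include women, men who are not azoospermic, men without such partners and subjects already off treatment. They bound the number and do not estimate it.

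**The case against.** The strongest reply is that the operative rule is clear. The programme is mandatory, it is specific to the drug, it has no azoospermia exception, and it is enforced at each supply by a signed form. Criterion 3(g) stands close to 3(e) in the same list. A reader might infer from the silence of 3(e) that the plan leaves open which text prevails, or that the main text as a whole is laxer than Appendix 6. The documents do not support either inference, for the reasons in step 4. This part of the objection stands, and it is why the point is minor.

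It can also be said that 3(e) waives only criterion 3(b)(ii), whose duration rests on half-lives plus sperm turnover, and that the Appendix 6 rule is a separate precaution, so a site can follow both. That is a workable reading, but nothing in 3(e) states the limit. Its words cover contraceptive requirements without qualification, and Appendix 6 places its male rule under contraception in at least one section.

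A third reply is that entry criteria no longer matter because enrollment closed on 23 August 2018. This lowers the stakes but does not remove them. The contraceptive criteria also govern conduct during and after treatment, and N-Pd and NE-Pd subjects may continue.

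Finally, a reader might infer that men have been left unprotected. The documents do not show that. Pomalidomide must not be dispensed to a man unwilling to follow the precautions. The last form signed also covers the 28 days after the last dose, although no new form is signed in that period because nothing is dispensed.

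**Conclusion.** The point holds as a minor internal inconsistency. On its natural reading, 3(e) gives azoospermic men an exemption that Appendix 6 does not allow. The mandatory programme in effect overrides it, so the remaining harm is contradictory site advice, with low residual risk to very few men who are under Appendix 6 and still on treatment or within 28 days of the last dose.

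The conclusion rests on two things: that the heterosexual-activity qualifier applies only to the women, and that no unseen text limits 3(e). The consent form, the patient information sheet and the local programmes were not available. It would go too far to say that all men in the trial face the conflict. Appendix 6 applies only in certain countries or regions, and for men under a local programme no conflict can be shown.

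**What to change.** Add one sentence to criterion 3(e): *This exemption does not apply to the condom or abstinence requirement for men taking pomalidomide (Appendix 6 or the applicable local programme).* Send a short notice to sites that have male subjects still on treatment or within 28 days of the last dose. While the criterion is open, the sentence on pregnancy testing that follows the exemption could be limited to women of childbearing potential, since read literally it also takes in azoospermic men; this is clerical.

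The cost is the sentence, the notice, and the step in Section 9.1.1: IRB/IEC submission for a protocol revision, or notification if the change is made by administrative letter. Data collection, endpoints and analyses do not change.
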